## **SHARE-S Aim 3: Shared Healthcare Actions & Reflections Electronic systems in Survivorship**

Wake Forest Baptist Comprehensive Cancer Center (WFBCCC)  
WFBCCC # 99420

Second, we will support patient engagement with SCP guidelines through self-management/health coaching. The first coaching call/videoconference will be 60 minutes and two subsequent coaching calls/videoconferences will be 30 minutes each. These sessions will be digitally recorded to review for treatment fidelity. Recordings will be made on a handheld device and saved to a Wake Forest server in a folder only accessible by the study team. Coaches will engage patients in a similar behavior change techniques described in the above mentioned exemplar one-session survivorship care planning intervention and other interventions that have informed recommendations included in survivorship clinical guidelines (i.e., goals and planning, feedback and monitoring, motivational interviewing). Coaches will emphasize supporting the autonomy of the patient in facilitating behavior change consistent with the principles of behavior changed outlined by Self-determination Theory. Other theoretical models for health behavior change generally choose the behavior of study and do not focus on peoples' motivation to engage in a particular behavior within their broader life context of other behaviors and how they contribute to broader goals. In this study, coaches will support participants in selecting personalized health goals to be consistent with our conceptual framework that is grounded in promoting patient choice. This approach was successfully implemented in another telephone lifestyle coaching study that provided participants with a range of topics for health goals that we adapted for use in this study: (1) Eat Wisely; (2) Be Physically Active; (3) Be Tobacco Free/Limit Alcohol; (4) Strengthen Social Connections; (5) Restore (e.g., manage Stress); (6) Get adequate Rest; (7) Engage in preventive Care; (8) Other Personal Development (e.g., spiritual, work, finance). Goals that emerged when considering life context from cancer survivors in our preliminary data informed adapted and added topics. The health coaching model adopted in this study includes training in mindfulness to enhance autonomy support.

Third, the patient receives a set of automated, tailored text messages (daily for 3 weeks after the first and second coach calls for a total of 6 weeks). SHARE-S offloads some communication about SCP, and enhances patient understanding and activation through the concept of spaced education, providing small pieces of information over time, and through brief assessments that can guide shared decision-making. Although evidence for these approaches exist, they have rarely been used in the context of cancer, and have not been applied to SCP. We adapted this text messaging intervention content with stakeholder input for use with cancer survivors. The system can send messages with a request for patient response (a two-way message) and store that information as an additional tailoring variable and as patient-generated data to be reviewed by the clinical teams. Messages can sent by text and will be based on the key components of SCP. We will also mail participants a packet of materials summarizing SCP and each of the topics introduced in coaching and text messages.

## **6.0 Outcome Measures**

## **SHARE-S Aim 3: Shared Healthcare Actions & Reflections Electronic systems in Survivorship**

Wake Forest Baptist Comprehensive Cancer Center (WFBCCC)  
WFBCCC # 99420

We will collect patient-reported data either remotely or in person at baseline (before the first coaching call) and follow-up (after the last coaching call).

### **6.1 Primary Outcome**

6.1.1. Feasibility as defined by the # participants enrolled/those e-referred.

### **6.2 Secondary Outcomes**

6.2.1. Other implementation outcomes

6.2.1.1. Adoption (e.g., #e-referred patients e-referred/those possible [based on chart review])

6.2.1.2. Acceptability (e.g., Acceptability of Intervention Measure, qualitative feedback from cancer survivors)

6.2.1.3. Appropriateness (e.g., Intervention Appropriateness Measure)

6.2.1.4. Other indicators of feasibility (e.g., number of participants enrolled per month, Feasibility of Intervention Measure, adherence rates, retention rates)

6.2.1.5. Fidelity (e.g., patient adherence to text responses, adherence to coaching sessions, length of coaching sessions, observational checklist completed for a subset of coaching sessions)

6.2.2 Service outcomes

6.2.2.1. Number of patients enrolled

6.2.2.2. Cancer types

6.2.2.3. Qualitative feedback on resources/processes utilized to enhance each of the chosen services

6.2.2.4. Adverse events related to the intervention will be described

6.2.2.5. Patient-reported measure of patient-centered communication and relatedness completed only at follow-up [HEAL Patient-Provider Connection]

6.2.3 Patient health outcomes (Self-reported)

6.2.3.1.1 Social role, physical functioning, anxiety, depression, fatigue, sleep disturbance, pain [PROMIS Profile 29; also used in clinical practice]. We will also assess the feasibility of pulling these data from the electronic health record.

## **SHARE-S Aim 3: Shared Healthcare Actions & Reflections Electronic systems in Survivorship**

Wake Forest Baptist Comprehensive Cancer Center (WFBCCC)  
WFBCCC # 99420

- 6.2.3.1.2 General health [one-item assessing perceived health].
- 6.2.3.1.3 Cancer-specific quality of life [Cancer-specific subscale of the QLACS]
- 6.2.3.1.4 Health behaviors [tobacco use, alcohol use, physical activity, nutrition, stress reduction]
- 6.2.3.1.5 Patient autonomy [Index of Autonomous Functioning]  
Self-efficacy for managing cancer [Self-efficacy to Manage Chronic Disease Scale] Mindfulness
- 6.2.3.1.6 Engagement with the survivorship care plan document (Self-reported reference to the care plan since it was given to them)
- 6.2.3.1.7 Satisfaction with care

### **6.2.4 Implementation Program**

- 6.2.4.1 Time from opening the study to first patient e-referred, time to 10th patient e-referred
- 6.2.4.2 When the survivor was e-referred (indicating whether it was when scheduling an appointment or required review of upcoming appointments). We will use a combination of field notes, electronic medical record notes, and direct observation to measure these milestones.
- 6.2.5 We will also adopt mixed-methods to assess select implementation outcomes as guided by the Consolidated Framework for Implementation Research (CFIR). We chose to incorporate CFIR because it will facilitate assessment of potential barriers and facilitators at multiple levels to help us prepare for implementing SHARE-S more widely.
- 6.2.6 Clinical factors (cancer type, time since diagnosis, prior treatments, comorbidities) abstracted from medical charts or self-reported.

We will also collect demographic characteristics for descriptive purposes (age, sex, rural-urban residence [classified by the Federal Office of Rural Health Policy definition of rural], race/ethnicity, marital status, education level, health literacy).

## **7.0 Analytic Plan**

### **7.1 Sample Size and Power**

## **SHARE-S Aim 3: Shared Healthcare Actions & Reflections Electronic systems in Survivorship**

Wake Forest Baptist Comprehensive Cancer Center (WFBCCC)  
WFBCCC # 99420

This pilot study has an accrual goal of 40 cancer survivors. The primary objective is to evaluate the feasibility of implementing SHARE-S into clinical care, where feasibility is defined based on the rate of enrollment. Assuming a negative binomial distribution and true enrollment rate of 30%, the probability that we would have to approach 164 or more people to recruit 40 is <0.05. Therefore, if we approach  $\geq 164$  participants to enroll 40, it is unlikely the true probability is above 30%, and we will conclude the study may not be feasible. Assuming we are able to enroll 40 survivors, with this sample size we will be able to estimate rates of interest within +/- 16% using exact 95% binomial confidence intervals. A sample size of 40 will also allow for reasonable estimates of SDs to be used to plan future studies.

The number of participants interviewed (12-24) will be determined when data saturation is reached. As is conventional for thematic analysis, we will conduct interviews until we think there is enough qualitative data to address issues related to the acceptability of study procedures. The study team's experience leads us to believe that 12-15 interviews from cancer survivors will be sufficient to achieve this objective. Our analyses of differences between cancer type will be for exploratory purposes and therefore data saturation using those variables is not the goal. If unexpected information emerges and our timeline allows, we will consider amending the protocol to recruit additional participants.

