#### 3.1 Primary Objective

- 3.1.1. To evaluate how successfully SHARE-S can be implemented into clinical care as characterized by rates of enrollment.

*We hypothesize >30% of patients e-referred to SHARE-S will enroll.*

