### **7.2 Data Analyses**

This study will provide quantitative data on implementation outcomes, service outcomes, patient health outcomes, implementation program information, and qualitative feedback on barriers and facilitators to guide future study planning. We will calculate 95% confidence intervals for each of the measures to determine the range of estimates that are consistent with our data. We will track the number of patients seen in the Survivorship Clinic, the number e-referred, and the percent who agree to enroll in SHARE-S. For those not enrolled, reasons will be summarized. The proportion of participants and corresponding exact 95% CI for participants who participated in SHARE-S and those who completed all assessments will be computed; we will also calculate the frequency of any adverse events and percent of participants who complete the follow-up visit to assess retention. We will use one-sample tests of binomial proportions to compare the recruitment rate to the hypothesized value of 30%. In exploratory analyses, we will compare participants who enroll versus decline, are non-adherent or who drop out by demographic characteristics and baseline scores of the measures (when applicable) using fisher's exact tests or Wilcoxon rank sum tests as appropriate. We will also investigate any differences in these analyses by cancer type.

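### The feasibility cut-off of 164 misses its stated 5% property by one person: under the plan's own model the probability is 0.0518, and the first cut-off below 0.05 is 165

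*Combined protocol and SAP*

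**What the plan says.** Section 7.1 (Sample Size and Power) fixes the target: "This pilot study has an accrual goal of 40 cancer survivors". It names the model and the reference rate, "Assuming a negative binomial distribution and true enrollment rate of 30" per cent, and states that "the probability that we would have to approach 164 or more people to recruit 40 is <0.05". The next sentence turns that number into a rule. If at least 164 people are approached to enrol 40, then "it is unlikely the true probability is above 30%, and we will conclude the study may not be feasible". Both sentences include 164 itself.

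The rule serves the primary objective in section 3.1: "We hypothesize >30% of patients e-referred to SHARE-S will enroll". Section 7.2 (Data Analyses) plans a test of the same rate: "We will use one-sample tests of binomial proportions to compare the recruitment rate to the hypothesized value of 30" per cent. It does not state whether that test is one- or two-sided, and it ties no feasibility conclusion or count cut-off to the result. No other section gives a different threshold or probability.

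**The concern.** The tail probability attached to 164 does not come out below 0.05 under the distribution the plan names. The value 164 is the 95th percentile of the number approached. That supports a rule triggered by more than 164, not one triggered by 164 or more. An off-by-one between a strict and an inclusive inequality is the likely cause, although the plan does not show its calculation and this remains an inference.

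This is the only count to which the plan ties a feasibility conclusion on the primary outcome. If the 40th enrolment came from the 164th person, the plan would lean towards not feasible although its own 5% criterion was not met. Any reader can check the figure, and moving the threshold once the count is known would look post hoc.

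**Working it through.** **Inputs, all from section 7.1**

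- Enrolments to reach: r = 40.
- True enrolment rate: p = 0.30.
- Distribution: negative binomial for T, the total number approached up to and including the 40th enrolment.
- Claim to check: P(T ≥ 164) < 0.05.

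**Formula.** At least n people are needed exactly when the first n − 1 people yield 39 enrolments or fewer. Hence

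P(T ≥ n) = P(Bin(n − 1, 0.30) ≤ 39).

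**The plan's own figure.** For n = 164: P(Bin(163, 0.30) ≤ 39) = 0.0518. The stated bound is not reproduced.

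**Neighbouring cut-offs**

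| Cut-off n | P(T ≥ n) | Below 0.05? |
|---|---|---|
| 163 | 0.0572 | no |
| 164 | 0.0518 | no |
| 165 | 0.0469 | yes |
| 166 | 0.0424 | yes |

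**Cross-check.** Counting failures instead, T ≥ 164 means at least 164 − 40 = 124 failures before the 40th success. The negative binomial survival function gives 0.05183 for at least 124 failures and 0.04691 for at least 125, in agreement with the table.

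**Percentile.** P(T ≤ 163) = 0.9482 and P(T ≤ 164) = 0.9531, so the 95th percentile of T is 164. It follows that P(T > 164) = 1 − 0.9531 = 0.0469. The claim is true for more than 164 and false for 164 or more.

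**Could another reading rescue the figure?**

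- *Normal approximation.* The mean is 40/0.30 = 133.33 and the SD is √(40 × 0.70)/0.30 = 17.64. The upper tail is 0.041 at 164, or 0.044 at 163.5 with continuity correction. Both are below 0.05, but the text names the negative binomial, and the uncorrected approximation already gives 0.046 at 163, so it would put the cut-off at 163.
- *Different target.* P(T ≥ 164) is 0.0354 with 39 enrolments and 0.0736 with 41. The first is below 0.05 but contradicts the stated goal of 40.
- *Fixed number approached.* P(Bin(164, 0.30) ≤ 40) = 0.0671, which is further above 0.05.

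None of these supports 164 as written.

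**What the two cut-offs say about the rate.** Inverting the same negative binomial model, the one-sided 95% upper bound solves P(Bin(n − 1, p) ≤ 39) = 0.05 for p:

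- n = 164 (observed rate 40/164 = 24.4%): upper bound 30.06%, so 30% is not excluded.
- n = 165 (observed rate 40/165 = 24.2%): upper bound 29.89%, so 30% is excluded.

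**Size of the discrepancy**

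- Excess over the stated bound: 0.0518 − 0.0500 = 0.0018, about 0.2 percentage points.
- Chance that the two rules disagree at a true 30%: P(T = 164) = 0.0518 − 0.0469 = 0.0049.

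**The case against.** The strongest reply concerns weight; the arithmetic is not in dispute.

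- **Almost no practical effect.** The rules differ at one value of T, which has probability 0.0049 at a true 30%. The goal of 40, the 16-month accrual period, the ±16% precision statement and the other analyses are unchanged. This stands.
- **Soft wording.** The plan says the study may not be feasible. That is an interpretive statement in a single-arm pilot, not a binding stopping rule, and the 0.05 only supports the word unlikely. An event with probability 0.052 is still unlikely. This stands as to consequence, but the plan asserts a strict inequality and that assertion is false.
- **The excess sits at the boundary.** The inference is about rates above 30%. At a true rate of 30.1%, P(T ≥ 164) is 0.0490, and at 31% it is 0.0288. That is correct. However, the plan computes its probability at 30%, so the claim has to hold there.
- **165 is correct only under the negative binomial.** If the number approached is treated as fixed, as the section 7.2 binomial test may do, the exact one-sided 95% upper bound for 40/165 is 30.36%, and 30% is first excluded at 40/168 (29.84%; 40/167 gives 30.01%). The two-sided exact p-value for 40/165 is 0.126. This stands as a qualification: the rule in 7.1 and the test in 7.2 can disagree, and correcting 164 does not resolve that. It does not rescue 164, since section 7.1 names the negative binomial and the fixed-number calculation moves the cut-off further up.
- **Not the only criterion.** Sections 3.1 and 7.2 also use the 30% value for the same rate. That is so, but neither gives a count or attaches a feasibility conclusion to one.

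**Conclusion.** The concern holds. With 40 enrolments, a true rate of 30% and the negative binomial distribution that section 7.1 specifies, the inclusive cut-off of 164 has probability 0.0518. The smallest inclusive cut-off below 0.05 is 165, at 0.0469. The error is carried from the probability statement into the decision rule.

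The result rests only on the plan's stated inputs and on each person approached being an independent trial with the same enrolment probability, which the negative binomial implies. The effect is very small and threatens neither the design nor the sample size. It is worth correcting because a stated error rate on a decision threshold for the primary outcome is wrong and the correction is trivial.

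**What to change.** In section 7.1, replace 164 by 165 in both sentences, so that the probability statement reads 165 or more and the rule reads ≥165. Writing more than 164 in both places is equivalent. The stated bound is then true, with probability 0.0469.

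Keeping 164 and reporting the probability as 0.052 would also remove the false statement, but it gives up the 5% criterion, so the first option is preferable. It would help to add that the cut-off is derived under the negative binomial model, because a fixed-number binomial test in section 7.2 can give a different answer near the threshold.

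The cost is one number in two sentences. Accrual goal, timeline and study operations are unaffected. The change should be made before the number approached is known.

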### **7.2 Data Analyses**

This study will provide quantitative data on implementation outcomes, service outcomes, patient health outcomes, implementation program information, and qualitative feedback on barriers and facilitators to guide future study planning. We will calculate 95% confidence intervals for each of the measures to determine the range of estimates that are consistent with our data. We will track the number of patients seen in the Survivorship Clinic, the number e-referred, and the percent who agree to enroll in SHARE-S. For those not enrolled, reasons will be summarized. The proportion of participants and corresponding exact 95% CI for participants who participated in SHARE-S and those who completed all assessments will be computed; we will also calculate the frequency of any adverse events and percent of participants who complete the follow-up visit to assess retention. We will use one-sample tests of binomial proportions to compare the recruitment rate to the hypothesized value of 30%. In exploratory analyses, we will compare participants who enroll versus decline, are non-adherent or who drop out by demographic characteristics and baseline scores of the measures (when applicable) using fisher's exact tests or Wilcoxon rank sum tests as appropriate. We will also investigate any differences in these analyses by cancer type.

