## **SHARE-S Aim 3: Shared Healthcare Actions & Reflections Electronic systems in Survivorship**

Wake Forest Baptist Comprehensive Cancer Center (WFBCCC)  
WFBCCC # 99420

Baseline analyses will include descriptive statistics of quantitative data on implementation outcomes, service outcomes, patient health outcomes, and background characteristics (i.e., clinical, demographic). The distributions of continuous variables will be examined to determine the presence of outliers and whether transformations are necessary for analysis. The primary goal of the statistical analysis of these measures will be to estimate standard deviations (SD) for use in future studies.

Additional analyses will include fitting mixed ANCOVA models (adjustment for baseline) to model the trajectory of patient health outcomes by time and group accounting for the repeated measures on a subject. The purpose of all of these models will be to obtain estimates of the SD of change adjusted for covariates of interest and the within-person correlation of the repeated measures, not to perform formal hypothesis testing. We will consider the different recall time frame for the quality of life measures when interpreting the results. In exploratory models we will examine the impact of adherence to SHARE-S on changes in the measures, subgroup analysis by cancer type, and we will examine the role of patient autonomy and self-efficacy as potential mechanisms. The purpose of these analyses will be to estimate SD and within-person correlation by subgroup and with adjustment for mechanisms; no formal hypothesis testing will be done.

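### The exploratory comparison in 7.2 treats adherence as an undefined non-adherent group, although the fidelity measures are graded; for moderate associations this gives up roughly 10-30 points of power on text replies

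*Combined protocol and SAP*

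**What the plan says.** Section 7.2 opens the relevant sentence with "In exploratory analyses, we will compare participants who enroll versus decline" and continues to those who "are non-adherent or who drop out by demographic characteristics and baseline scores of the measures (when applicable) using fisher's exact tests or Wilcoxon rank sum", with the choice between the two methods left to suit the data. Three contrasts therefore share one method: enrolment against decline, non-adherence, and drop-out.

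The measures behind the word adherence are listed in 6.2.1.5: "Fidelity (e.g., patient adherence to text responses, adherence to coaching sessions, length of coaching sessions, observational checklist completed for a subset of coaching sessions". Section 5.3 gives their range. For coaching, "The first coaching call/videoconference will be 60 minutes and two subsequent coaching calls/videoconferences will be 30 minutes each", which makes three sessions. Texts go out "daily for 3 weeks after the first and second coach calls for a total of 6 weeks". Section 5.3 adds that the system can request and store a reply, and section 8.0 lists adherence and text responses as a stored data item.

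No section defines non-adherent, gives a cut-off, or says whether the label refers to texts, coaching or both. Later in 7.2 adherence appears again: "In exploratory models we will examine the impact of adherence to SHARE-S on changes in the measures". The form of the variable is left open there, and formal testing is ruled out.

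**The concern.** Enrolment and drop-out are yes/no events, so Fisher's exact and rank-sum tests between groups suit them. Adherence is not such an event. A participant can attend one session or three, and can answer few texts or nearly all. Reducing that to a group discards the ordering within each side of the cut, which is costly with 40 people at most. It also merges texts and coaching, on which the same person may differ, and it ties the result to a cut that the plan does not state.

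At stake is how well the pilot can describe which enrolled patients engage less. That is one of several pieces of information meant to guide the larger study.

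**Working it through.** **Inputs from the plan**
- Enrolled participants: 40 (section 7.1, "This pilot study has an accrual goal of 40 cancer survivors").
- Coaching sessions: 1 + 2 = 3, so the count runs from 0 to 3 (5.3).
- Texts: 2 periods × 3 weeks × 7 days = 42 messages (5.3). The number that request a reply is not stated.
- Power, effect size and alpha for this comparison: none stated.

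**The plan's own figure at n = 40.** Section 7.1 gives a precision of ±16%. The exact 95% interval at 20/40 is 33.8% to 66.2%, a half-width of (66.2 − 33.8)/2 = 16.2 points. This reproduces, but it concerns rates and says nothing about the adherence comparison.

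**Simulation model (assumptions, not in the documents).** Baseline score x is standard normal. Latent adherence is y = ρx + √(1 − ρ²)·e, with e standard normal. Graded analysis: Spearman correlation of x with adherence. Split analysis: Wilcoxon rank-sum on x between the non-adherent (lowest 20-50%) and the rest. n = 40, two-sided 5%, 2,000-3,000 runs per scenario. Loss = graded power − split power.

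*Near-continuous adherence, half labelled non-adherent*

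| ρ | Graded | Split | Loss (points) |
|---|---|---|---|
| 0 | 5.4% | 4.6% | (type I error) |
| 0.2 | 22.5% | 16.5% | 6.0 |
| 0.3 | 43.8% | 30.0% | 13.8 |
| 0.4 | 66.5% | 48.7% | 17.8 |
| 0.5 | 88.1% | 72.5% | 15.6 |

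Over 20-50% non-adherent, the loss is 6-8 points at ρ = 0.2, 14-20 at 0.3, 18-30 at 0.4 and 16-31 at 0.5.

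*Text count with 35% at the ceiling*

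| Cut | ρ = 0.3 | ρ = 0.4 | ρ = 0.5 |
|---|---|---|---|
| about 20% | 39.4 − 22.1 = 17.3 | 65.3 − 38.5 = 26.8 | 86.4 − 57.4 = 29.0 |
| about 30% | 40.6 − 28.8 = 11.8 | 63.7 − 43.6 = 20.1 | 85.4 − 66.8 = 18.6 |
| 50% | 39.2 − 28.2 = 11.0 | 64.1 − 49.1 = 15.0 | 86.2 − 72.5 = 13.7 |

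*Coaching sessions, 0-3.* With 70% attending all three and non-adherent meaning any session missed, the loss against a baseline score is 1-5 points (for example 50.3 − 46.1 = 4.2 at ρ = 0.4). Other session distributions and cuts give 8-21 points.

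*Two-level characteristic.* Here the comparison is rank-sum on graded adherence against Fisher's exact test on the split. For an evenly divided characteristic and standardised differences of 0.4-1.0, the loss on near-continuous adherence is 9-38 points. For sessions with 70% attending all and any session missed as the cut, it is 8-10 points. Part of this is the conservatism of Fisher's test, which rejects in only about 3-4% of null samples here.

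**Denominator for texts.** The second three weeks of texts follow the second coach call. Suppose, as an assumption, that reply-requesting texts are spread evenly over the six weeks. Someone who misses call 2 but answers every text received scores 100% of texts sent, but 21/42 = 50% of texts planned. Someone who never takes call 1 scores 0/0 on texts sent and 0% on texts planned. With the planned denominator, the gain from the graded analysis is still about 12-27 points at ρ = 0.3-0.5.

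**The case against.** The strongest reply is that the comparison is labelled exploratory, has no alpha or decision rule, and feeds no primary conclusion. Section 7.1 bases the sample size on enrolment, on the precision of rates and on standard deviations. All of that stands. Graded adherence is itself underpowered for modest associations: about 44% at correlation 0.3 and about 22% at 0.2.

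The second reply is that the size rests on assumed effects, cuts and ceilings, and on a smooth monotone model that favours rank correlation. If people either engage or do not, the gain may shrink. This also stands, so the loss has to be stated conditionally.

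The third is that one format for three kinds of non-engagement is a simple presentation, and that the plan uses adherence elsewhere and holds interviews on barriers and facilitators (3.2.5). The simplicity is real. However, the later models ask whether adherence relates to change in outcomes, not who adheres. Choosing between Fisher and rank-sum as appropriate still leaves only group comparisons.

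The fourth is that a proportion of texts answered misranks or drops people who miss a coach call. That is correct for a denominator of texts sent. It is met by a fixed planned denominator.

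**Conclusion.** The point holds as a low-cost improvement to an exploratory analysis. Adherence is graded by design, is used in this comparison as an undefined group, and can be analysed on its recorded scale. For text replies against a baseline score at n = 40, with assumed correlations of 0.3-0.5 and 20-50% labelled non-adherent, the split loses roughly 10-30 points of power. The loss is about 6-8 points at correlation 0.2, and as little as 1-5 points for coaching sessions if most attend all three.

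Three stronger readings are tempting, and the documents do not support them:
- That the split costs 10-30 points in every case. The plan states no effect size or cut, and the coaching result shows that the loss can be trivial.
- That every use of adherence in the plan is yes/no. The later exploratory models leave its form open.
- That the plan records counts, or intends to pick the cut after seeing the data. The graded scale is a fair inference from 5.3, 6.2.1.5 and 8.0, but no scoring rule is given. The missing cut-off only leaves a later choice possible.

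**What to change.** In 7.2, keep Fisher's exact and rank-sum tests for enrol versus decline and for drop-out versus retained. For adherence, replace the group with two measures analysed separately:

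- (a) coaching sessions attended, 0 to 3;
- (b) two-way texts answered, as a proportion of all reply-requesting texts planned for the full six weeks. Texts not sent because a coach call was missed count as unanswered, so that participants who do not engage are neither dropped nor scored 100%.

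Relate each to baseline scores and age by Spearman correlation with a 95% confidence interval, and to categorical demographics by rank-sum or Kruskal-Wallis tests on the adherence measure. Report all of this as exploratory estimates. A proportion adherent may still be given descriptively.

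The cost is a few sentences of wording, with no new data, visits or participants. The downside is two adherence measures instead of one label, hence more exploratory comparisons, and correlations that are slightly less simple to present than two groups.
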